12.4.2 Analysis of the Key Secondary Endpoints

50% and 75% response

The two key secondary endpoints, 50% response (Weeks 1-12) and 75% response (Weeks 1-12) will be analysed using logistic regression. The model will include baseline MMDs as a continuous covariate, and treatment and stratification factor (MHDs at baseline: $\leq 14 />14$) as factors. The SAS[®] code for these key secondary analyses is shown in Appendix IV.

The logistic regression model will be fitted using the maximum likelihood (ML) method and the logit link function.

The odds ratios for eptinezumab 300 mg and eptinezumab 100 mg compared to placebo will be estimated from the model and presented with p-values based on the likelihood ratio test and 95% CIs based on the profile likelihood.

The nominal p-values comparing each dose of eptinezumab to placebo will be presented. The comparisons will be part of the testing strategy described in Section 12.2.

In addition, the differences in response proportions between each dose of eptinezumab and placebo will be presented.

Change from Baseline in the number of MMDs (Weeks 13-24)

Changes from Baseline in MMDs at Weeks 1-4, Weeks 5-8, Weeks 9-12, Weeks 13-16, Weeks 17-20, and Weeks 21-24 will be analysed using the same methodology as described in Section 12.3.2 for the primary endpoint.

The mean differences between each dose of eptinezumab and placebo will be estimated based on the least squares means for the treatment-by-visit interaction in the MMRM model. The estimates will be presented with nominal p-values and 95% CIs. The comparisons will be the contrasts between each dose of eptinezumab and placebo averaged across Weeks 13-24. The comparisons will be part of the testing strategy described in Section 12.2.

Change from Baseline in HIT-6

Changes from Baseline in HIT-6 total score at weeks 4, 8, 12, 16, 20, and 24 will be analysed using the same methodology as described in Section 12.3.2 for the primary endpoint, replacing baseline MMD score with baseline HIT-6 score in the model.

The mean differences between each dose of eptinezumab and placebo will be estimated based on the least squares means for the treatment-by-visit interaction in the MMRM model. The estimates will be presented with nominal p-values and 95% CIs. The comparisons will be the contrasts between each dose of eptinezumab and placebo at Week 12. The comparisons will be part of the testing strategy described in Section 12.2.

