16.8.4 Analysis of the Key Secondary Endpoints

- For the key secondary endpoints based on response rates, treatment effects compared to placebo will be analysed using logistic regression. The model will include baseline MMDs as a continuous covariate, and treatment and stratification (MHDs at baseline: ≤14 />14) as factors.
- The change from baseline in HIT-6 score for the Placebo-controlled Period will be analysed using a mixed model repeated measures (MMRM) including baseline HIT score as covariate, treatment, country, stratification factor (MHDs at baseline: ≤14 />14), and week as fixed factors. In addition, the model will include treatment-by-week interaction, baseline HIT-6 score-by-week interaction, and stratum-by-week interaction. An unstructured covariance structure will be used to model the within-patient errors. The Kenward-Roger approximation will be used to estimate denominator degrees of freedom. Treatment effects will be calculated based on least squares means for the treatment-by-week interaction estimated at Week 12.
- Change from baseline in the number of MMDs (Weeks 13-24), will be analysed using the same MMRM methodology as for the primary endpoint. The comparisons will be the contrasts between each dose of eptinezumab and placebo averaged across Weeks 13-24.

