	 Change from baseline in the number of monthly days with use of acute migraine medication Change from baseline in the number of monthly migraine days with use of acute migraine medication PGIC score Change from baseline in the number of monthly migraine days in patients with MOH MBS score Change from baseline in monthly number of Migraine attacks for each 12-week period Change from baseline in monthly number of Headache episodes for each 12-week period Change from baseline in the MSQ v2.1 sub-scores Change from baseline in the EQ-5D-5L VAS score HCRU Change from baseline in the WPAI sub-scores
 Safety Objective To evaluate the safety and tolerability of eptinezumab To evaluate the long-term safety and tolerability of eptinezumab 	 Safety Endpoints Adverse events Absolute values and changes from baseline in clinical safety laboratory test values, vital signs, weight, and ECG parameter values Potentially clinically significant clinical safety laboratory test values, vital signs, weight changes, and ECG parameter values Development of specific anti-eptinezumab antibodies (ADA) including neutralizing antibodies (NAbs) Columbia-Suicide Severity Rating Scale (C-SSRS) score

2 Study Design

This is an interventional, multi-national, multi-site, randomized, double-blind, placebocontrolled Phase IIIb study designed to demonstrate efficacy and safety of eptinezumab for migraine prevention in patients with unsuccessful prior preventive treatments. The placebocontrolled period will be followed by an extension period where all patients will receive active treatment to assess the long-term safety, tolerability and effect of eptinezumab.

The target population for this study is defined as patients with chronic migraine (CM) or episodic migraine (EM), as outlined in the IHS ICHD-3 guidelines¹ with documented evidence of migraine occurring on \geq 4 days per month prior to screening as confirmed via prospectively collected information in the eDiary during the Screening Period, and with documented evidence of failure to 2-4 different preventive migraine medications in the past 10 years. The aim is that approximately 40% of the randomized patients are patients with EM.

It is planned that 840 patients will be randomly allocated to one of three treatment groups: eptinezumab 300 mg, eptinezumab 100 mg, or placebo, in a ratio of 1:1:1.

Randomization will be stratified by country and monthly headache days (MHDs) at baseline (\leq 14 MHDs/>14 MHDs).

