4.5 Definition of Migraine and Headache Days

For the purpose of endpoint derivations, the following definitions of migraine and headache days will be used. The definition of a migraine day reflects the strategy chosen to handle the intercurrent event of using acute migraine medication in the primary estimand, as outlined in Sections 12.3.1 and 12.3.3.

In this document, the term headache will encompass both headaches and migraine headaches. Migraine headaches (henceforth simply referred to as "migraines") are a subgroup of headaches with characteristics outlined below (Section 4.5.1). Using this definition, we have that all migraines are headaches but not all headaches are migraines.

Headaches will be self-reported by the patient using an electronic headache diary (eDiary). The eDiary is split into two parts, the headache diary and the evening diary. The headache diary is the part of the eDiary where the start and stop date and times of experienced headaches are recorded along with headache characteristics used for classifying headaches as migraines, and the evening diary is the part of the eDiary that patients are expected to complete each day during the study regardless of whether or not they experienced a headache on that day.

Randomization is stratified by Monthly Headache Days (MHDs) at baseline (≤ 14 MHDs/>14 MHDs). The stratum is based on a calculation performed directly in the eDiary at Baseline. The eDiary uses an algorithm described in the Project Design Specification (PDS), a document providing the technical specifications for the set-up of the eDiary, for determining whether a day in the screening period classifies as a day with a headache or a day with a migraine. Patients are deemed eligible if, according to this algorithm, they fall into the criteria for CM or EM as defined in inclusion criterion 10 in the *Clinical Study Protocol* (ed. 1.0 and 2.0), i.e:

- For patients with CM: Migraine occurring on ≥8 days and headache occurring on >14 days.
- For patients with EM: Migraine occurring on ≥4 days and headache occurring on ≤14 days

In this document, whenever stratum or stratification factor is mentioned, the reference is to this classification into EM and CM that was used for randomization.

The PDS definition of a migraine day can be seen in Appendix III.

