12.3.4 Rationale for Selected Analysis Method for the Primary Endpoint

The MMDs are considered continuous data, and they are analysed using methods based on observations following a normal distribution. Given the repeated observation of normally distributed data, an MMRM analysis using all available data has been chosen for the primary analysis. Covariates are included in the model based on an approach including key factors representing study design features (month, treatment, MHD stratum, country), and baseline MMD score to account for differences in baseline MMDs and its predictive ability. When the MMRM analysis includes the individual factors mentioned as well as interaction of month and treatment, month and baseline score, and month and stratum, and applies an unstructured covariance, as described in Section 12.3.1, it allows for flexibility in modelling the development over time and similarly provides robust estimation, even under some deviation from the assumption of normality.

The use of MMRM combined with the rules for handling missing data in this set-up allows for inclusion of the majority of the patients, even if they only have limited data observed.

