12.4.3 Rationale for Selected Analysis Method for the Key Secondary Endpoints

The rationale for the selected analysis method for change from Baseline in the number of MMDs (Weeks 13-24) and change from Baseline in HIT-6 is covered by Section 12.3.4.

The logistic regression model has been chosen for its ability to provide estimates of treatment effects, as well as adjust for the effects of strata and covariates. Covariates are included in the model based on an approach including key factors representing study design features/strata (stratum and treatment), and baseline MMDs to account for its predictive ability for the response.

Although it is recognized that adjustment for predictive covariates will always, in contrast to classical linear regression models, result in a loss of precision (or no change) of the estimates, the adjustment for predictive covariates will result in greater efficiency/higher power when testing for a treatment effect in a randomized study.^{2,3} The chosen covariate is considered to

be highly predictive for the response, and thus the logistic regression model is considered valid as a key secondary analysis model.

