For patients with any post-baseline suicidal ideation or behaviour in the Placebo-controlled Period (C-SSRS scores of 1 to 10), listings will be provided based on APRS including all C-SSRS scores prior to entering the Extension Period for those patients for inclusion in the *CSR*.

A similar listing will be provided for patients with any post-baseline suicidal ideation or behaviour in the Extension Period including all the C-SSRS scores for those patients for inclusion in the *addendum to CSR*.

14 Blinded Data Reviews

The quality of the study will be overseen by performing blinded data reviews during the conduct of the study. The reviews may include, but are not limited to, data quality, protocol adherence, and the appropriateness of design assumptions, including the sample size assumptions.

An independent Safety Data Monitoring Committee (DMC) will regularly monitor the patients' safety data according to the *DMC Charter*. The DMC will have access to unblinded information for the double-blind treatment for each patient. Members of the DMC will not be involved in other study-related tasks.

15 Interim Analyses

See Section 18.

16 Sample Size Considerations

The two prior eptinezumab Phase III studies, PROMISE-1 performed in an EM population and PROMISE-2 performed in a CM population, had the following effect sizes for the primary endpoint when compared to placebo (standard deviations):

- EM: 100 mg 0.69 (3.1), 300 mg 1.11 (3.1)
- CM: 100 mg 2.03 (5.8), 300 mg 2.60 (5.8)

The power was determined by simulating the testing strategy (10000 simulations) assuming normal distributions with similar mean and SD for continuous endpoints and similar success rates as the response variables in the Phase III studies for the corresponding population (EM or CM) without assuming the variables to be correlated. With 280 patients per treatment group, assuming that 40% of the patients will be from the EM population and 60% from the

CM population, and that 2% of the patients not having a post-baseline assessment of the primary endpoint, simulations show that the power for the test of the primary endpoint is approximately 94% for the comparison of 100 mg to placebo and 99% power for the comparison of 300 mg to placebo. The individual key secondary endpoints had a power of at least 68% for showing an effect, with a combined power of 58% for seeing an effect for all primary and key secondary endpoints and both doses in the testing strategy.

17 Statistical Software

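### The logistic models for 50% and 75% response leave out country, a randomisation factor that the MMRMs include; adding it would be a cheap, small gain in power

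*SAP*

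**What the plan says.** SAP section 2 gives two stratification factors: "Randomization will be stratified by country and monthly headache days (MHDs) at baseline". Protocol 3.1 says the same. The MMRM for the primary endpoint (SAP 12.3.2) has country as a fixed effect, and HIT-6 uses the same methodology. SAP 12.3.4 justifies this by including "key factors representing study design features (month, treatment, MHD stratum, country".

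The responder models are narrower. SAP 12.4.2: "The model will include baseline MMDs as a continuous covariate, and treatment and stratification factor (MHDs at baseline". Protocol 16.8.4: "The model will include baseline MMDs as a continuous covariate, and treatment and stratification (MHDs at baseline". Country is not included by implication, because SAP 4.5 says that "whenever stratum or stratification factor is mentioned, the reference is to this classification into EM and CM that was used for randomization". The rationale in SAP 12.4.3 refers to "key factors representing study design features/strata (stratum and treatment" plus baseline MMDs. It also states that "the adjustment for predictive covariates will result in greater efficiency/higher power when testing for a treatment effect in a randomized study". It does not mention country.

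The logistic code that SAP 12.4.2 places in Appendix IV was not readable in the copy used here, so the omission is taken from the model text. That text is explicit and the same in both documents.

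**The concern.** When randomisation is balanced within a factor that predicts outcome, the treatment estimate varies less than an analysis ignoring that factor assumes. The unadjusted standard error is then too large and the test slightly conservative. The SAP accepts this reasoning for the MMRMs and states the power argument for logistic models, but applies it to only one of its two stratification factors.

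The responder tests matter to the sequence in SAP 12.2. The 50% response test is Step 2 for 300 mg and Step 4 for 100 mg, and a failure at either stops all later formal testing. The 75% response test sits in the Holm groups at Steps 5 and 6 and may have to meet α/3.

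**Working it through.** **1. The plan's own power figure.** Inputs from SAP 16: 280 per arm less 2% = 274.4; 40% EM, 60% CM; effects (SD) for EM 0.69 and 1.11 (3.1), for CM 2.03 and 2.60 (5.8); two-sided 0.05.
- Mean effect, 100 mg: 0.4×0.69 + 0.6×2.03 = 1.494. 300 mg: 0.4×1.11 + 0.6×2.60 = 2.004.
- Pooled SD: √(0.4×3.1² + 0.6×5.8²) = 4.90. SE: 4.90×√(2/274.4) = 0.418.
- Power: Φ(1.494/0.418 − 1.96) = 94.6% and Φ(2.004/0.418 − 1.96) = 99.8%. The SAP states 94% and 99%, so its primary figures reproduce.

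**2. Power of the responder tests.** The SAP says only that "The individual key secondary endpoints had a power of at least 68% for showing an effect", with 58% combined power. It gives no response rates as numbers, so neither figure can be reproduced. The 68% is a floor across all key secondary tests. If it were the stand-alone power of both 50% tests, their joint power would be about 0.53 (correlation 0.5 from the shared placebo arm). Multiplied by 0.945 for both primary tests, that gives 0.50, below the stated 58%. Beyond that the gate power depends on whether 68% is a stand-alone or an in-sequence figure, which the SAP does not say. No value is claimed here.

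**3. Size of the loss.** The documents do not give the number of countries, the country effect or the response rates. All of the following are assumptions: 823 patients in three arms; 15 countries of unequal size; permuted blocks of 6 within country × MHD stratum; countries under 20 patients pooled; control response 25% or 40% (50% endpoint) and 12% (75% endpoint); a baseline MMD effect on response. Country effects are normal on the log-odds scale. With 25% average response, 95% of countries lie at 16-38% for SD 0.3, 11-47% for SD 0.5 and 6-62% for SD 0.8.

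Points of power gained by adding country to the likelihood-ratio test of one dose against placebo (about 6,000 trials per setting; two values are for 25% / 40% control response):

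| Test, power as planned | SD 0 | SD 0.3 | SD 0.5 | SD 0.8 |
|---|---|---|---|---|
| 50% response, about 75% | 0.6 / 0.7 | 1.2 / 1.2 | 1.7 / 2.2 | 3.8 / 3.6 |
| 50% response, about 90% | 0.3 / 0.4 | 0.7 / 0.7 | 0.7 / 1.2 | 2.0 / 2.3 |
| 50% response, about 95% | 0.2 / 0.2 | 0.4 / 0.3 | 0.7 / 0.7 | 1.1 / 1.2 |
| 75% response at α/3, about 70% | 0.7 | 1.1 | 2.0 | 4.1 |
| 75% response at α/3, about 90% | 0.3 | 0.5 | 0.9 | 2.0 |

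The SD 0 column is not a real gain. It reflects the slightly liberal test in step 5 and should be subtracted: for example, 1.7 − 0.6 = 1.1 points at SD 0.5, 75% power and 25% control response.

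**4. Independent check.** A separately written simulation (2,500 trials per setting, 15 countries, no pooling, baseline terms fitted but given no effect on response) gave these powers without → with country:
- Control 30%, active 39.9%: SD 0.3, 68.1 → 68.9%; SD 0.5, 68.2 → 70.6%; SD 0.8, 66.0 → 70.6%.
- Control 30%, active 43.3%: 90.7 → 91.1%; 90.0 → 91.3%; 89.4 → 91.4%.
- Control 10%, active 17.1%: 69.3 → 69.9%; 71.4 → 72.7%; 71.1 → 73.8%.

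At SD 1.0 the gain was 3.0 to 6.8 points. A further run at 30% control response and about 75-78% power gave 0.8-1.3, 1.6-2.0 and 4.5 points at SD 0.3, 0.5 and 0.8.

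The second simulation also shows the mechanism. At 30% control response, 39.9% active and SD 0.5, the mean log odds ratio moved from 0.442 to 0.472 and its actual SD from 0.181 to 0.193. The ratio hardly changed (0.442/0.181 = 2.44; 0.472/0.193 = 2.45). Adding country therefore mainly removes the overstatement of the standard error.

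**5. Type I error** (10,000 trials per setting) at SD 0, 0.3, 0.5, 0.8:
- 50% test, nominal 5%: 5.0, 5.1, 4.7, 4.1% without country; 5.3, 5.5, 5.3, 5.4% with (simulation SE about 0.22).
- 75% test, nominal 0.05/3 = 1.67%: 1.6, 1.9, 1.9, 1.4% without; 1.8, 2.1, 2.1, 1.7% with (SE about 0.13).

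**The case against.** The strongest reply is that nothing is broken. Protocol and SAP agree, and the choice looks deliberate. For the CMH tests, SAP 12.5 says that it adjusts for one of the stratification factors, so the authors knew there were two. Covariates are chosen model by model: the MHD analysis in SAP 12.5 keeps country and drops the stratum. SAP 12.3.4 explains the MMRM and sets no rule for other models. The planned 50% test holds its level, whereas the test with country runs slightly above it, and the 50% test is a confirmatory gate. The gain rests on inputs that are not in the documents.

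Most of this stands, and it is why the point is minor. The SAP does not break a rule of its own. The liberality is real, but only a few tenths of a point. It does not remove the case for adjustment, because the power gain remains after the SD 0 column is subtracted whenever country predicts response.

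A reader might infer that leaving out a stratification factor inflates type I error or biases the odds ratio. Neither follows. The error of ignoring country is on the conservative side, and the odds ratio without country is a less conditional quantity, not a wrong one. A reader might also apply the 68% to the gates and conclude that they are weakly powered; SAP 16 does not support that.

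**Conclusion.** The point holds as a minor improvement to the analysis. Country is a design factor that the MMRMs use and the two responder models do not, and SAP 12.4.3 does not say why. If country predicts response beyond baseline MMDs and the MHD stratum, the 50% and 75% response tests give up a little power: about 0-1 point for small country differences (log-odds SD 0.3), 1-2 points for moderate ones (SD 0.5), and 3-5 points only for extreme ones (SD 0.8) in a test with about 70-75% power. In better powered tests the loss is smaller. If country does not predict response, nothing is lost.

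These sizes depend on the assumed response rates, the 15 countries and the country effect. The direction, and the absence of type I inflation, do not depend on those choices within the range tried.

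**What to change.** If the blind is intact, add country as a factor to the 50% and 75% response models in SAP 12.4.2 and Protocol 16.8.4. Pool small countries by a rule fixed on blinded patient counts, for example into the region variable that SAP section 8 already summarises. State that the odds ratio is then conditional on country, and keep the planned model as a sensitivity analysis.

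The cost is one model term and one pooling rule, with no new data. The odds ratio changes meaning slightly and is a little less precise, sparse countries need pooling (mainly for 75% response), and the likelihood-ratio test with many country terms runs a few tenths of a point above nominal.

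If the placebo-controlled data are already unblinded, leave the testing strategy as planned and report the country-adjusted model as supplementary only. This is probably the case that applies: the change summary in Protocol edition 3.0 records that sponsor personnel reviewing the study report were unblinded after the placebo-controlled database lock.

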12.4.3 Rationale for Selected Analysis Method for the Key Secondary Endpoints

The rationale for the selected analysis method for change from Baseline in the number of MMDs (Weeks 13-24) and change from Baseline in HIT-6 is covered by Section 12.3.4.

The logistic regression model has been chosen for its ability to provide estimates of treatment effects, as well as adjust for the effects of strata and covariates. Covariates are included in the model based on an approach including key factors representing study design features/strata (stratum and treatment), and baseline MMDs to account for its predictive ability for the response.

Although it is recognized that adjustment for predictive covariates will always, in contrast to classical linear regression models, result in a loss of precision (or no change) of the estimates, the adjustment for predictive covariates will result in greater efficiency/higher power when testing for a treatment effect in a randomized study.^{2,3} The chosen covariate is considered to

be highly predictive for the response, and thus the logistic regression model is considered valid as a key secondary analysis model.

